C.6. Prelim Data #6: mHealth-based Med Adherence and BP Control in Ghanaian Stroke Patients: In a pilot RCT,^{44,45} we evaluated the feasibility of an mHealth technology-enabled, nurse guided intervention in improving BP control among 60 recent Ghanaian stroke survivors; 30 each in the intervention & standard of care (SC) arms. Participants in the intervention arm received a Blue-toothed UA-767Plus BT BP device & smart phone for monitoring, reporting BP measurements & med intake under nurse guidance for 3 months vs. SC. Tailored motivational text messages were delivered based upon levels of adherence to the medication intake. To control for attention exposure, the SC arm received SMS messages dealing with healthy lifestyle behaviors but not with med adherence. The PINGS intervention was stopped after month 3 & both groups were followed up until month 9. Primary outcome measure was BP control (<140/90mmHg at month 9). Secondary outcome measures included: (i) medication adherence measured using the Medication possession ratio (MPR) at month 9 and (ii) technological glitches. Outcomes: (1) BP control at month 3 by Intention to treat analysis was 20/30 (66.7%) vs 14/30 (46.7%), p=0.12 in the intervention and control arms respectively at interim analysis at end of intervention.⁴⁴ At month 9, proportion on the intervention vs. controls with systolic BP<140mmHg was 22/30(73.3%) versus 13/30(43.3%), p=0.035 in favor of the PINGS intervention.⁴⁵ (2) Medication possession ratio scores at month 3 were better in the intervention arm (0.88 ± 0.40) vs. SC (0.64 ± 0.45) arm (p=0.03), & at month 9 was (0.95 ± 0.16) vs (0.98 ± 0.24), p=0.56. These pilot trial findings support testing an mHealth intervention aimed at improving BP control after stroke in an under-resourced region.^{44,45} We observed a potential signal of efficacy with the intervention, which we have refined further to test within a larger definitive clinical trial in the current proposal.

D. SOLID COLLABORATIVE RESEARCH TEAM

Our interdisciplinary team has been involved in several projects of direct relevance to PINGS-2 research focus. Our interdisciplinary team represents experts in medicine, nursing, public health, health communication, and information technology. (see bios).

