E.4.1. Design: PINGS-2 is a phase III randomized, open label, blinded endpoint clinical trial to evaluate the efficacy and acceptability of a nurse-led, mHealth technology-centered, multi-level integrated approach in achieving sustained BP control among recent stroke survivors with hypertension encountered at primary, secondary and tertiary medical centers in Ghana, a LMIC in SSA compared with usual care. This is a 2-arm RCT involving 500 stroke survivors with individual participant randomization.

E.4.2. Eligibility: *Inclusion* – (i) age \geq 18 years (stroke is commoner above this age cut-off); (ii) male or females (sex is a biologic variable of interest); (iii) recent stroke (within one month of symptom onset)- stroke may be ischemic or hemorrhagic based on brain imaging or diagnosed clinically using the locally validated version of the 8-item questionnaire for verifying stroke free status (8-QVSFS) when neuroimaging is not feasible¹¹⁹; (iv) uncontrolled HTN (SBP \geq 140 mmHg at both the last clinical encounter post-stroke and the eligibility screening visit) - SBP is used as the selection variable since most African hypertensives <60 years have systolic or combination systolic/ diastolic HTN and for most patients, controlling SBP also results in DBP control;¹⁷⁰⁻¹⁷² (v) patients or family carers should own a basic mobile phone that can receive text/audio messages.

Exclusion – Any condition that would limit participation in follow up assessments, such as severe cognitive impairment/dementia (MMSE ≤ 24).

E.4.3. Training of Physicians and Nurse navigators on Standard of care for post-stroke vascular risk factor management using expert consensus guidelines: Physicians and nurse navigators at all 10 study sites will receive an initiation and annual training sessions on standard practices for post-stroke vascular risk factor management using local & current international guidelines¹⁷⁰ to be delivered by [name] (MPI) to minimize variability in provider practices across study sites and enhance patient safety.

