E.4.8. Outcome and Mediator Measures: Primary outcome is proportion of participants with BP<140/90mmHg at 12-months which is the major modifiable step to stroke event rate reduction. We will also conduct longitudinal comparisons of systolic BP in the intervention vs. usual care groups over the course of follow-up evaluations. Participants will be given an appointment encounter solely for collecting evaluation data at the times listed in Figure 1. Trained assessors with no contact to the PINGS study team will perform all study measurements. Potential mediator/moderators of risk factor control and implementation outcomes will also be collected.

E.4.8.1. Physiological/Laboratory Measures

i. BP measurements: Three readings will be taken by trained study coordinators using an automated BP monitor with the patient seated comfortably for 5 min prior to the measurements, following guidelines.^{174,175} Average of the last 2 BP readings will be used as the measure for each visit. Uncontrolled BP is defined as average clinic systolic BP \geq 140 mm Hg or diastolic BP \geq 90 mmHg per guidelines.¹⁷⁶

E.4.8.2. Self-report Measures and Other Information: Self-report measure outcomes will be assessed using validated questionnaires (see Table 3) administered by trained Research Assistants blinded to allocation of study participants to record responses of participants.

Table 3. PINGS-2 Outcomes and Mediators

| Outcomes | Brief Description |
|---|---|
| Systolic Blood Pressure (Primary outcome) | Target goal of <140/90 mmHg measured at baseline, months 3, 6, 9 and 12. Measured by blinded evaluator using an automated BP monitor. |

| | |
|--|---|
| Self-management outcome (Secondary outcome) | Compared between the two groups using the validated Hypertension Self-care Profile questionnaire (HBP SCP) with items that compositely assesses behavior, motivation and self-efficacy of hypertension management. Assessed at months 4, 8 and 12 ($\alpha=.83-.93$, $r=.64$) ¹⁸¹ |
| Medication adherence (Secondary outcome) | Measured using Medication possession ratio ¹⁷⁷ and 14-item Hill-Bone compliance (HBC) to high blood pressure therapy scale with items that assess medication adherence, clinic appointments and salt intake ¹⁷⁸ assessed at months 3, 6, 9 and 12 ($\alpha=.76-.83$, $r=.64$) ^{179,180} MPR and HBC will be measured in both PINGS and usual care arms at stated time points. |

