E.4.9.2. Power and Sample Justification: Our sample size calculation and power analyses are based on the proportion with BP<140/90mmHg at 12 months, the premier modifiable risk factor for stroke. In a recent pilot study^{44,45} by this group in Ghana, where this proposed study will take place, 60 subjects (30 per group) were randomized to PINGS & control arms with BP<140/90 mmHg at month 9 was 46% versus 40% after withdrawing the PINGS intervention after 3 months.⁴⁵ We anticipate at least 60% BP control rate in the intervention arm (lasting for 12 months) versus 44% control in the usual care arm, using a type I error of 0.05, a power of 90%, & a two-sided test, we need a total of 406 subjects. Assuming 20% loss to follow up, the conservative target for enrollment is 500. We conservatively expect ~50% will not meet eligibility criteria or may decline to participate, so we can potentially recruit over 500 patients from ~ 5,550 stroke patients encountered at 10 hospitals over 4 years.

E.4.10. Data Management and Analysis

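### Table 3 labels the primary outcome as systolic blood pressure, and the model named for Aim 1 suits a continuous outcome, while E.4.8 and the sample size use the proportion below 140/90 mmHg at 12 months

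*Combined protocol and SAP*

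**What the plan says.** Section E.4.8 is explicit: "Primary outcome is proportion of participants with BP<140/90mmHg at 12-months". Its next sentence gives systolic pressure a supporting role: "We will also conduct longitudinal comparisons of systolic BP in the intervention vs. usual care groups". Section E.4.8.1 defines control on both components. The sentence that opens "Uncontrolled BP is defined as average clinic systolic BP" goes on to count a patient as uncontrolled if systolic is at least 140 or diastolic is at least 90 mmHg, using the mean of the last two of three readings. Aim 1 refers to blood pressure control at 12 months, E.8.1 calls one year the primary time point, and E.4.9.2 sizes the trial on the proportion below 140/90 at 12 months.

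Table 3, the outcomes table, differs. Its first row is headed "Systolic Blood Pressure (Primary outcome". The description beside that label reads "Target goal of <140/90 mmHg measured at baseline, months 3, 6, 9 and 12". So the row pairs a systolic name with a two-component target. It does not say whether the outcome is a mean or a proportion, and it does not single out month 12.

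Section E.4.10.1 tests the hypotheses of Aims 1 and 2 with a linear mixed model for the 12-month outcome, with the baseline value as covariate. Later in the same section, binary outcomes are assigned to generalized linear mixed models with a logit link. The section does not say which of the two gives the primary test.

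**The concern.** The outcomes table is where an analyst or a site looks up what is primary, and here it names the variable that E.4.8 treats as additional. Alone, that could be a loose label. Together with the model for Aim 1 it is more, because the label and the linear model both fit systolic pressure analysed as a continuous measure, while E.4.8 and the sample size fit a binary endpoint. The primary outcome and its primary test should be fixed before data are seen, so that neither can be chosen afterwards. As written, someone could defend a systolic analysis as primary by pointing to Table 3 and E.4.10.1, or a binary one by pointing to E.4.8 and E.4.9.2.

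The choice may affect the result. The pilot month-9 figures in C.6 and E.4.9.2 show a large difference on a systolic threshold and a small one on the combined threshold.

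**Working it through.** **1. Which endpoint the trial is sized on.** Inputs from E.4.9.2: 60% vs 44% below 140/90, two-sided 0.05, 90% power. E.4.9.1 gives 1:1 allocation. With pooled variance under the null and no continuity correction:

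n per arm = [1.960·√(2·0.52·0.48) + 1.2816·√(0.60·0.40 + 0.44·0.56)]² / 0.16²
= [1.3848 + 0.8938]² / 0.0256 = 5.192 / 0.0256 = 202.8, so 203 per arm and 406 in total.

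This matches the stated 406 exactly. The trial is sized on the binary 140/90 endpoint.

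**2. Whether the Aim 1 model fits that endpoint.** E.4.2 requires systolic pressure of at least 140 mmHg at the last clinical encounter and at screening. Under E.4.8.1 every such patient is uncontrolled. If the baseline reading is the screening reading, baseline control status is the same for everyone and cannot serve as a covariate; if it is taken separately, it will vary little. Adjustment for a baseline value therefore makes sense for continuous pressure and hardly at all for the binary outcome.

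**3. The places side by side.**

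| Place | What it points to |
|---|---|
| E.4.8, first sentence | Binary, 140/90, month 12 |
| E.4.8, second sentence | Systolic as an additional comparison |
| E.4.8.1 | Two-component definition of control |
| Aim 1, E.8.1 | Control at 12 months; one-year time point |
| E.4.9.2 | Binary, 140/90, month 12 |
| Table 3, label | Systolic, scale not stated |
| Table 3, description | 140/90 target, five visits |
| E.4.10.1, model for Aims 1 and 2 | Continuous outcome with baseline covariate |
| E.4.10.1, later text | Logit model for binary outcomes |

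**4. Pilot illustration, month 9, 30 per arm.**

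- Systolic below 140 (C.6): "systolic BP<140mmHg was 22/30(73.3%) versus 13/30(43.3%), p=0.035". Difference 22/30 − 13/30 = 30.0 points. Fisher's exact test gives p=0.035, matching the printed value. Standard error √(0.733·0.267/30 + 0.433·0.567/30) = 0.121, so the Wald 95% interval is 6 to 54 points.
- Below 140/90 (E.4.9.2): "BP<140/90 mmHg at month 9 was 46% versus 40" per cent. The printed difference is 6 points. No count out of 30 rounds to 46%: 13/30 is 43.3% and 14/30 is 46.7%. If the counts were 14/30 and 12/30, the difference is 2/30 = 6.7 points, Fisher p=0.79, standard error √(0.467·0.533/30 + 0.40·0.60/30) = 0.128, and Wald 95% interval −18 to 32 points.

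The documents give no pilot means or standard deviations for systolic pressure, so the continuous reading cannot be checked in the same way.

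**The case against.** The strongest reply is that the endpoint is already settled. The Table 3 row itself cites 140/90, so a reader of the table does not arrive at a systolic-only threshold. E.4.8, E.4.8.1 and E.4.9.2 agree on 140/90, and Aim 1 and E.8.1 agree on one year. The five times in Table 3 are measurement visits, not five primary endpoints. On this view only a row label needs correcting.

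Much of that stands, and it rules out several stronger readings.

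- A reader might infer that systolic below 140 is a rival primary endpoint. No section names it as this trial's primary. The literal reading of the label is continuous systolic pressure, so the 30-point pilot difference does not measure the discrepancy.
- A reader might infer that the two definitions lead to opposite conclusions. Both pilot differences favour the intervention, and the intervals overlap widely. The pilot was small, and month 9 fell six months after its intervention stopped.
- A reader might take the pilot to refute the remark in E.4.2 that "for most patients, controlling SBP also results in DBP control". It does not. On the assumed counts, and since everyone below 140/90 is also below 140 systolic, 14 of 22 (64%) and 12 of 13 (92%) with systolic control were also below 140/90, which is 26 of 35 (74%) overall. The remark also only justifies systolic pressure as the selection variable.
- A reader might see selective reporting in C.6, which states 140/90 at month 9 as the pilot's primary outcome and then gives only the systolic result at that time. The combined result is disclosed in E.4.9.2 of the same document.

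What the reply does not remove is the conflict between the Table 3 label and E.4.8, or the linear model with a baseline covariate named for testing Aim 1.

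**Conclusion.** The inconsistency is real and should be corrected. The weight of the plan, including a sample size that reproduces exactly, favours the proportion below 140/90 at 12 months. The Table 3 label and the Aim 1 model in E.4.10.1 point towards continuous systolic pressure, and nothing in the plan says which place takes precedence.

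It would go too far to say that the trial's result depends on which place is followed; the documents support only that it could. The pilot contrast of 30 points against 6 as printed (6.7 on assumed counts) illustrates the risk. It does not estimate it, because it compares two thresholds and not a threshold with a continuous outcome. The p-value of 0.79 and the 14-of-22 figure rest on the assumption that 46% and 40% stand for 14/30 and 12/30 in the same 60 patients; the 30-point difference and its p=0.035 do not.

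**What to change.** 1. In Table 3, rename the primary row as the proportion with systolic below 140 mmHg and diastolic below 90 mmHg, each from the mean of the last two readings, at month 12.
2. Add a separate secondary row for systolic pressure over months 3, 6, 9 and 12, and state that it cannot replace the primary outcome.
3. In E.4.10.1, state that the primary test of Aim 1 uses the binary model with logit link, and confine the linear mixed model to continuous outcomes. Baseline control status should not be the baseline covariate in the primary model, for the reason given in step 2 of the working.
4. Leave the sentence in E.4.2 unchanged.

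The cost is wording only. The readings are already scheduled, the sample size already rests on this endpoint, and no visit or measurement is added. What is given up is the freedom to choose the primary measure later.

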E.4.5.2. Provider Level: Providers will follow care protocols based on expert consensus practice guidelines to address HTN management. A task-shifting strategy using nurse navigators will be used in this study to deliver primary care to stroke patients with HTN. Male and female nurse navigators will be recruited and trained for this study. The Nurse navigators will receive approximately 80 hours of intensive training over a 2 week period prior to initiating study at each study site. They will participate in didactic and group-based learning on the fundamentals of non-communicable diseases, health promotion/disease prevention and patient centered communication. They will receive instructions on how to reinforce patient adherence to antihypertensive regimens through patient- and family-centered approaches & also receive training on proper BP measurement technique. If a PINGster's mean BP exceeds thresholds (e.g., BP >180/ 105 or <100/75 mmHg), the patient will contact the **nurse navigator** via a phone call or text message for advise on what to do. The nurse navigator will follow an algorithm to address issues relating to non-adherence, side effects, insufficient dosing of antihypertensive med, and so forth. In instances where a clinic visit is required to address BP threshold breeches or health related issues, the nurse navigator will arrange with the research team to have patient seen.

E.4.6. Usual care Protocol: Inclusion criteria include owning a cell phone with at least SMS and voicemail. To control for attention exposure, they will get SMS messages dealing with healthy lifestyle behaviors (smoking, diet, physical activity) but not with med adherence, HTN or stroke related issues. Similar to the intervention group, the usual care patient will have a total of 5 follow-up study visits during which various study outcomes (see Figure 1) will be assessed. Usual care participants will also be contacted by phone monthly to confirm contact information and to inquire about hospitalizations.

E.4.7. Health care access during and after intervention: Both during and after the intervention, study participants will be followed up at the study sites at scheduled visits for evaluation of study outcomes and have access to the study physicians for *unscheduled visits for any health urgencies or emergencies, in particular where BP breeches require hospitalization for urgent management*.

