| Cardiovascular ED encounters and re-hospitalizations (Secondary outcome) | To be assessed via once monthly calls to patients and/or carers over 12 months of follow up in both the PINGS and usual care groups. Patient carers in both arms will also be encouraged to contact study team within 48 hours of hospitalizations for prompt and blinded adjudication of all potential CVD ED encounters to minimize reporting bias between the two groups. |
| Major Adverse Cardiovascular Events (Secondary outcome) | Major Adverse Cardiovascular events (MACE) to be assessed include recurrent stroke: fatal/ severely disabling stroke or non-fatal stroke; Co Disease: Acute STEMI/NSTEMI, sudden cardiac deaths. MACE will be confirmed by a blinded adjudicator by reviewing where available clinical notes supported by investigations e.g. CT scan, EKGs, review of death certificates or verbal autopsy if death occurs outside hospital. |
| Health Literacy in HPT/stroke (Mediator) | Self-Report: HTN/stroke Knowledge questionnaire ($r=.70$), ^{182,183} Health literacy questionnaire ($r=.74, .82$), ^{184,185} Assessed at months 0, 6, 12. |
| Health-related quality of Life (secondary) | The EQ-5D questionnaire, ¹⁸⁶ will assess state of health of study participants at baseline and Month 12. |
| Disability/Functional status (Mediator) | Functional status after stroke will be assessed by Research Assistants using the Modified Rankin Scale ^{187,188} with a scores ranging from 0 to 6, where 0=no functional limitation and 6 = death. Assessed at months 0, 3, 6, 9 and 12. |
| Sex, Age, cultural, socio-economic Factors, study site (mediator) | Assessed based on self reports at baseline. Cultural factors to assess include language spoken at home, religious observances, acceptance of gender roles; occupation, religious beliefs and dietary practices. |
| Side effects, Adverse events | As reported by participants during follow-up using NCBI toxicity criteria |

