E.8.2. Individual Randomization: We are randomizing patients instead of clusters, because it is the most statistically efficient method for showing efficacy & would require the smallest sample size.²⁰⁹ Cluster randomization is appropriate when contamination threat is high²¹⁰ but we believe contamination threat is minimal given that the Home BP monitor, protocol-based phone calls to nurse navigators, & educational audio messages will apply to the intervention group with a very low probability of the usual care group having access to all 3 components of the PINGS intervention.

E.9. Work Plan and Timetable: PINGS-2 is expected to last a total of 4.5 years from initiation of the first study site to completion of the last clinical trial participant. Activities in the first 9 months of Year 1 will include development of a detailed manual of operations, obtaining IRB and Ghana Foods and Drugs Authority approvals for the study protocol, setting up logistics, formation of a Data Safety Monitoring Board, development of a data management system, and training of study coordinators and nurses.

E.9.1. Pre-trial pilot testing of modified PINGS intervention: We will run a small pilot to pre-test the PINGS intervention among ≈ 10 stroke survivors (1 from each study site) for 1-month trial to trouble-shoot the intervention & make further modifications if required before starting the main trial by month 9 in year 1.

E.9.2. Recruitment & Follow-up of PINGS study: Anticipated *monthly* recruitment rate is ~1 participant (from each of 6 primary-level centers), 2 participants (from each of 2 secondary-level centers), up to 4 participants (at each of 2 tertiary-level centers) over 36 months will provide an estimated 648 participants (greater than 500 in the proposed study) for the clinical trial. Trial enrollment will be staggered by center, starting with two centers at a time, and for all centers initial recruitment targets for first few months lower than average targets to enable study sites get used to the trial processes and incorporate the study into their center. Recruitment will be stopped once the planned number of RCT participants is attained per site. The implementation strategy aims will start from year 1 through to year 5 to capture the change process during implementation. Data cleaning, final data analyses and manuscript preparation will take place in Months 54-60.

Table 4. Schedule of Activities

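### Non-serious adverse events have no stated common elicitation, and only the PINGS arm has a nurse line and home BP monitoring, so the arm comparison of these events is at risk of unequal ascertainment

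*Combined protocol and SAP*

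**What the plan says.** The last row of Table 3 (PINGS-2 Outcomes and Mediators) covers side effects and adverse events: "As reported by participants during follow-up using NCBI toxicity criteria". Toxicity criteria grade an event once it is known; they do not say how it is elicited. Most other rows of the table name an instrument, time points or a blinded assessor.

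The contact channels are described elsewhere:

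- **PINGS arm.** Under E.4.5.1, participants receive a home monitor, are encouraged to measure at least weekly, and are told to call the nurse navigator beyond limits given as examples (>180/105 or <100/75 mmHg). Under E.4.5.2, "The nurse navigator will follow an algorithm to address issues relating to non-adherence, side effects, insufficient dosing of antihypertensive med, and so forth". E.8.2 places these calls in one arm: "protocol-based phone calls to nurse navigators, & educational audio messages will apply to the intervention group".
- **Usual care.** E.4.6 says: "Usual care participants will also be contacted by phone monthly to confirm contact information and to inquire about hospitalizations".
- **Both arms.** Table 3 runs the monthly calls about cardiovascular ED encounters and re-hospitalizations "over 12 months of follow up in both the PINGS and usual care groups". E.4.6 adds: "Similar to the intervention group, the usual care patient will have a total of 5 follow-up study visits". E.4.7 gives study participants in general unscheduled access to study physicians for urgent problems.

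E.4.8.2 says that self-report outcomes are collected by validated questionnaires "administered by trained Research Assistants blinded to allocation of study participants to record responses of participants". It does not name adverse events.

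**The concern.** A PINGS participant who feels dizzy, or whose home monitor shows a low reading, has a prompt to call and a nurse whose algorithm deals with side effects. A usual-care participant with the same symptom has no equivalent route for a non-urgent complaint. If the adverse-event record takes in whatever reaches study staff, the arms may differ in how often events are heard and not only in how often they occur.

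The intervention aims at tighter BP control, so low BP and drug side effects are the natural harms to look for. With unequal capture, an excess in PINGS could be an artefact. A true excess could equally be explained away as better reporting. E.4.10.1 says that all outcomes will be modelled by regression, and adverse events sit in the outcomes table, although no specific adverse-event test is given. The DSMB (E.5) reviews safety twice a year.

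**Working it through.** **Step 1. Is there a plan figure to reproduce?** No. The documents give no adverse-event rate, capture rate or safety power. The sample size in E.4.9.2 concerns BP control and does not bear on this point.

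**Step 2. Compare the channels by arm.**

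| Channel | PINGS | Usual care | Source |
|---|---|---|---|
| Study visits | 5 | 5 | E.4.6 |
| Follow-up assessor blinded | yes | yes | E.4.8, E.4.9.1 |
| Monthly hospitalization calls | yes | yes | Table 3, E.4.6 |
| Blinded adjudication of cardiovascular ED encounters and MACE | yes | yes | Table 3 |
| Unscheduled access to physicians | yes | yes | E.4.7 |
| Nurse line, algorithm covers side effects | yes | no | E.4.5.2, E.8.2 |
| Home BP monitor with prompt to call | yes | no | E.4.5.1, E.8.2 |

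The asymmetry lies in the last two rows. It affects mainly non-serious events, because the serious cardiovascular ones are actively sought or adjudicated blind in both arms.

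**Step 3. Illustrate the size. Every rate here is an assumption.** Let the true 12-month risk p be the same in both arms, with 250 per arm (500 randomized 1:1), and let a fraction c of affected participants be recorded.

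- Apparent risk ratio = (p × c_PINGS) / (p × c_usual) = c_PINGS / c_usual
- Apparent excess = p × (c_PINGS − c_usual)
- Chance of a falsely significant PINGS excess (two-sided 0.05) = Φ[(excess − 1.96 × SE0) / SE1], where SE0 uses the pooled proportion and SE1 the two separate ones.

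Taking c_usual = 70%:

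| c_PINGS | Risk ratio | Excess at p = 10 / 20 / 30% | Chance of false PINGS excess |
|---|---|---|---|
| 70% | 1.00 | 0 / 0 / 0 points | 2.5% (half of 0.05) |
| 80% | 0.80/0.70 = 1.14 | 1 / 2 / 3 points | 6% / 9% / 12% |
| 90% | 0.90/0.70 = 1.29 | 2 / 4 / 6 points | 13% / 23% / 35% |

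One cell in full, for p = 20% and c_PINGS = 90%:

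- Recorded proportions are 0.18 and 0.14 (45 and 35 of 250), so the excess is 0.04.
- SE0 = √(2 × 0.16 × 0.84 / 250) = 0.0328.
- SE1 = √((0.18 × 0.82 + 0.14 × 0.86) / 250) = 0.0327.
- (0.04 − 1.96 × 0.0328) / 0.0327 = −0.74, which gives 23%.

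**The case against.** The strongest reply is that the plan already has a symmetric route: equal visit numbers, and follow-up assessors who do not know the allocation. The adverse-event row does not exclude questioning at those visits, and Figure 1 and the body of Table 4 (the schedule of activities), neither of which is visible in the text reviewed, may give adverse-event times. This stands in part. A missing schedule should not be held against the plan. But times alone would not show that both arms are asked the same questions, and the sentence on blinded assistants concerns validated questionnaires, while the adverse-event row names none.

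A second reply is that the nurse line is not a general side-effect line, since its stated trigger is a BP threshold breach, and that nothing says nurse calls feed the adverse-event record. Both points are correct. They make the bias conditional on a data flow that the plan leaves open; they do not close it.

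Three stronger readings are tempting and not supported:

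- A reader might set the nurse line against usual-care calls limited to hospitalizations. Table 3 runs the hospitalization calls in both arms, so they are not the asymmetry.
- A reader might infer that all safety events rest on participant report alone. Cardiovascular ED encounters and MACE do not. For the ED encounters, Table 3 states that the aim of prompt, blinded adjudication is to limit reporting bias between the arms.
- A reader might treat the missing by-arm table of extreme BP readings as an error. The limits are examples that prompt a call, not a safety endpoint, and visit BP is already compared by arm over time.

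**Conclusion.** The point holds as a risk, not as a demonstrated bias. The visible text states no common elicitation of non-serious adverse events, and two channels that can bring such events to light exist only in PINGS. Unequal capture is plausible and would probably raise the PINGS counts. The direction is not certain: a problem settled by the nurse might go unmentioned at a visit, and 60% against 70% capture, for example, would give an apparent ratio of 0.60/0.70 = 0.86.

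No size can be derived from the documents. The ratios of 1.14 and 1.29 only restate the assumed capture rates, and equal capture gives 1.00. To say that the safety comparison is biased, or that the DSMB will see unbalanced data, would go beyond the documents. The primary outcome, the sample size and the adjudicated cardiovascular outcomes are unaffected. This is a cheap improvement to the plan.

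**What to change.** 1. Have the blinded research assistants ask about adverse events with one fixed, prompted form, identical in both arms, at the existing month 3, 6, 9 and 12 assessments. State this in the adverse-event row of Table 3.
2. Record the source of every event: scheduled visit, nurse line or other unscheduled contact.
3. Base the between-arm comparison on the scheduled-visit data, and list nurse-line and other unscheduled reports separately.
4. Optionally, tabulate by arm the blinded visit BP readings that fall beyond the plan's own call-in limits. These data are already collected.

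If Figure 1 or Table 4 already gives adverse-event times, only the form, the source field and the analysis rule need adding. The cost is a few minutes per visit and one short form. Recorded events in usual care will rise, which is the intended effect. The sample size and clinical management do not change.
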